9.3.2 OAC exposure

New OAC exposure is defined as a single or series of dispensation of an OAC starting in the period from 1 January 2014 to end of study period. The duration of the observation period together with the pack size of each prescription will be used to calculate the length of a patient's OAC exposure. To ensure a minimum of one month follow-up data for all subjects on OAC treatment, inclusion (cut-off index OAC date) will be stopped one month before the end of available follow-up data.

For each dispensation, the OAC days of supply will be computed using information on date of dispensation, the number of packages and the pack-size dispensed. Since NOACs are prescribed in a fixed dose, the number of days of supply strictly corresponds to amount dispensed accounting for a recommended frequency of daily dosing. The NorPD contains information on tablet strength, pack-size and number of packages dispensed, and we assumed, according to the labelling, twice daily dosing for apixaban and dabigatran and once daily dosing for rivaroxaban, e.g. a patient supplied one package of a 100 tablet package of rivaroxaban will have a supply lasting for 100 days, whereas a 100 tablet package of apixaban will provide a supply lasting 50 days.

Computing the warfarin supply is not straightforward as we lack information on both dosing instructions and International Normalised Reference values (INR) in the registries.

Two different methods will be applied to compute the warfarin exposure;

1. EMR data (from cohort 2) holds information on both INR and dosing. Median mg/day of warfarin will be computed in relation to age (in 5-year categories) and gender (females and males). The median mg/day will be used as a basis for computing the warfarin supply in cohort 1.
2. Registry data (from cohort 1) using the length of each time interval in days between dispensation and corresponding dispensed warfarin amount for the time interval will be used to compute the median daily warfarin use for each patient. The calculated median mg/day for all patients using warfarin in the study period, in relation to age group and gender as with method 1, will subsequently be used in the computation of warfarin supply for each dispensation.

Similarly, the same methods will be used to set the end of OAC supply date during the pre-index period to be able to determine if a patient was OAC naïve or not (≥ 365 days without OAC supply prior to index date).

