The duration of dispensation (DoD) will be set as the date of a dispensed prescription plus the estimated duration of that prescription (duration of OAC supply estimated from the dispensed pack-size and strength).

The following rules applies:

1. If the next dispensed prescription was for the same OAC within 30 days after end of DoD there was a continuous treatment
2. If a new dispensed prescription for another OAC occurred within DoD or within 30 days after end of DoD there was a switch in OACs (switching date = date of dispensation)
3. If the next dispensed prescription was for the same OAC more than 30 days after end DoD there was a discontinuation (discontinuation date = date of DoD + 30 days)

A 30-day gap period is included to take into account incomplete adherence to treatment. The figure underneath displays the three different scenarios. In sensitivity analyses the gap period will be varied from 30 days to 0 days, 15 days and 60 days, respectively.

[figure not shown]

Figure 4: Definition of continuation, switch and discontinuation

Patients to be included in the effectiveness and safety analysis should have a supply of OAC covering the event, plus a 30 days grace period for those patients discontinuing their therapy. Any event happening after the date of discontinuation plus 30 days or after a switch in OAC therapy will not be included.

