9.3.3 Estimation of OAC adherence

Proportion of days covered (PDC) will be estimated for each individual from the index medication date and onwards. The PDC is defined as the number of days that the index medication was on hand during the time period divided by the total number of days in the period. For instance if the length of the time period is 100 days and the NOAC supply covers 50 days, the adherence is estimated to 50%.

Likewise, the age- and sex-specific median doses of warfarin (using the two methods described in 9.3.2) will be used to calculate to warfarin supply.

If the OAC supply last longer than the study period the adherence is set to 100%. The proportion of days covered (PDC) will take into account the patient's entire follow-up period, defining end of study period as death, end of study, migration, discontinuation or switch of OAC therapy. In addition to the entire period, adherence will also be estimated at fixed time intervals after OAC index date, i.e. 3 months (90 days), 6 months (180 days), and 9 months (270 days), 1 year (365 days), 2 years (730 days) and 3 years (1095 days).

Consecutive dispensations of the same OAC will be combined and corrected for overlap. For treatment gaps equal or less than 30 days of the previous OAC dispensation it is assumed the patient is on continuous therapy. The length of the gap period will be varied in sensitivity analyses down to 0 and 15 days and up to 60 days.

Some patients switch to another NOAC during follow-up and the day of switch will be defined as the end of the time period. Separately, the PDC for use of any OAC during the study period will be estimated, which accounts for therapy switching during follow-up.

PDC will be estimated as the mean PDC for each OAC as well as grouped into four categories of high adherence (≥ 0.80), moderate adherence (0.50-0.79), low adherence (0.20-0.49) and poor adherence (<0.20). Adherence will also be reported as dichotomized using the conventional PDC of <0.80 or ≥ 0.80 as cutoff. Percentage point differences between OAC user groups will be presented. Analyses of OAC adherence will account for differences in follow-up time and baseline characteristics, such as standard and reduced dosing level.

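### Whole-period PDC stops at discontinuation, so it cannot fall below s/(s + 30) for fills of s days, and the planned low and poor adherence categories are nearly unreachable

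*Protocol*

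**What the plan says.** Protocol section 9.3.3 gives the measure: "The PDC is defined as the number of days that the index medication was on hand during the time period divided by the total number", where the denominator counts every day of that period. The whole-period version runs over follow-up, "defining end of study period as death, end of study, migration, discontinuation or switch of OAC therapy".

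Section 9.3.2 supplies the discontinuation date. If the same drug is next dispensed more than 30 days after the end of the dispensed supply, "there was a discontinuation (discontinuation date = date of DoD + 30 days").

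Section 9.3.3 adds three rules:
- On gaps: "For treatment gaps equal or less than 30 days of the previous OAC dispensation it is assumed the patient is on continuous therapy".
- On sensitivity analyses: "The length of the gap period will be varied in sensitivity analyses down to 0 and 15 days and up to 60 days".
- On supply running past the end: "If the OAC supply last longer than the study period the adherence is set to 100" per cent.

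The same section also plans PDC at 90, 180, 270, 365, 730 and 1095 days after the index date. It does not say whether these windows end at discontinuation.

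PDC is to be reported as a mean, in four categories (0.80 and above, 0.50-0.79, 0.20-0.49, below 0.20), dichotomised at 0.80, and as percentage-point differences between drug groups. Section 9.7 repeats the four-level report for each NOAC. Section 8.3 plans to relate adherence level to the rates of ischemic stroke and bleeding.

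**The concern.** A patient who stops filling prescriptions leaves the PDC calculation 30 days after the supply ends. The long uncovered stretches that would produce a low PDC are removed by the rule that defines the period. What remains is a measure of refill punctuality while still on treatment, with a floor set by the length of each fill.

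Three planned uses suffer:
- The lower two of the four categories have almost nothing to hold.
- Differences between drugs mix adherence with days supplied per fill.
- The adherence-outcome analysis works with a variable that has little or no low range.

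Section 7 of the protocol names missing adherence information as a limitation of the earlier Norwegian registry study, so this is a gap the study means to fill.

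**Working it through.** **Inputs, all from the protocol.** PDC is days on hand divided by days in the period, and the period ends at discontinuation (9.3.3). Discontinuation is end of supply plus 30 days (9.3.2). Sensitivity gaps are 0, 15 and 60 days (9.3.2 and 9.3.3). As illustrations of supply, "a patient supplied one package of a 100 tablet package of rivaroxaban will have a supply lasting for 100 days", while "a 100 tablet package of apixaban will provide a supply lasting 50 days" (9.3.2).

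**1. The protocol's own example.** Section 9.3.3 takes 50 days of supply in a 100-day period: 50/100 = 50%, which reproduces. Under the stopping rule, however, a single 50-day supply with no refill ends the period on day 80, and PDC is 50/80 = 62.5%.

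**2. The floor.** Take k fills of s days, each followed by at most g uncovered days (a longer gap ends the period at g days). Covered days are k × s and the period is at most k × (s + g), so

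minimum PDC = s/(s + g).

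With unequal fills, the shortest fill gives the bound. A simulation of random refill patterns reached minima equal to this formula.

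| Gap g (days) | s = 100 | s = 50 |
|---|---|---|
| 0 | 100/100 = 1.00 | 50/50 = 1.00 |
| 15 | 100/115 = 0.87 | 50/65 = 0.77 |
| 30 (main) | 100/130 = 0.77 | 50/80 = 0.63 |
| 60 | 100/160 = 0.63 | 50/110 = 0.45 |

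The sensitivity analyses therefore move the floor itself. At a 0-day gap every patient scores 100% by construction.

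**3. What the lower categories require at the 30-day gap.**
- PDC below 0.50: s/(s + 30) < 0.50 gives s < 30 days.
- PDC below 0.20: s/(s + 30) < 0.20 gives 4s < 30, so s < 7.5 days.

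For instance, 28-day fills can reach 28/58 = 0.48, and 7-day fills 7/37 = 0.19.

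**4. Difference between drugs.** With 100 tablets per fill for both drugs, the floors are 76.9% (once daily) and 62.5% (twice daily). That is 14.4 percentage points apart for the least adherent pattern the rule can record.

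**5. Early stoppers.** A patient with 120 gap-free days who then stops for good scores 120/150 = 0.80 and is classed as highly adherent.

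**6. Fixed windows not cut at discontinuation.** For one 100-tablet fill and no refill:
- 180 days: 100/180 = 0.56 (rivaroxaban) and 50/180 = 0.28 (apixaban).
- 365 days: 100/365 = 0.27 and 50/365 = 0.14.

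The low and poor categories become reachable. If these windows are cut at discontinuation, the floors in step 2 return.

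**The case against.** The strongest reply is that much of the remedy is already in the protocol. The stopping rule is attached to the whole follow-up, and the fixed intervals are introduced as additional to it. If they run on past discontinuation, they can show low adherence, and that detail could be settled in the SAP. This stands in part, since the right windows are already listed. But the whole-period rule is stated in the protocol, and nothing says which version feeds the categories, the drug comparison or the outcome analysis.

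It can also be argued that on-treatment PDC is a legitimate measure, consistent with censoring at discontinuation elsewhere in the study. That is fair if it is labelled as such, but it does not suit categories that reach below 0.20.

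Several stronger readings are tempting, and the documents do not support them:
- **Low adherence can never be observed.** It can, with fills under 30 days, with 50-day fills at the 60-day gap (0.45), and in fixed windows that are not cut.
- **The 100% rule causes the problem.** It does not create the floor. It can be read as ordinary truncation of supply at the end of the period. Only a literal reading lets a long last fill erase earlier gaps.
- **PDC is 100% for everyone in the main analysis.** That needs gap days to count as covered. The definition counts days on hand, and the sentence on continuous therapy more naturally says whether a treatment episode continues.
- **The twice-daily drugs will look 14 points less adherent.** The 100-tablet packs are only an example. The gap in floors needs equal tablet counts per fill, and a floor bounds the worst pattern without giving the mean.

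One further caveat: the discontinuation rule in 9.3.2 is worded for patients who later refill. Read literally, never-refillers would not discontinue and could have a low PDC. The same section's grace period for patients who discontinue points the other way.

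**Conclusion.** The point holds for the whole-period PDC. As defined, it cannot fall below s/(s + 30): 0.77 for 100-day fills and 0.63 for 50-day fills. The low and poor categories can be reached only with fills under 30 and under 7.5 days. The floor moves with the gap length chosen in the sensitivity analyses and differs between drugs whenever days supplied per fill differ. The planned adjustment for follow-up time and baseline characteristics does not remove a bound built into the definition.

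This rests on two assumptions: patients who never refill are treated as discontinued at end of supply plus 30 days, and gap days count as uncovered. Actual fill lengths are not given in the protocol, so how many patients sit near the floor is unknown. For the fixed-interval PDC the finding is conditional: it shares the defect only if its windows are cut at discontinuation. The consequences fall on descriptive results and one exploratory objective; no primary result uses PDC.

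**What to change.** - Make the already planned fixed-interval PDC the basis for the four categories, the between-drug differences and the adherence-outcome analysis.
- State that these windows end only at death, emigration, switch or end of data, and not at discontinuation. Section 9.3.2 calls a change of drug a switch only within supply or the following 30 days, so also say how a later start of another drug is handled.
- Count gap days and days after discontinuation as uncovered.
- Reword the 100% rule so that supply is truncated at the window end and earlier gaps still count.
- Report persistence separately. If the on-treatment PDC is kept, label it as such and do not apply the low and poor categories to it.

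The cost is protocol and SAP wording and some reprogramming of data already collected. Reported adherence will be lower than under the current definition.

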9.3.4 Outcome measures

9.3.4.1 Outcome definitions effectiveness

Cohort 1 and 2 (same for both cohorts):

The main efficacy endpoint is ischemic stroke defined by the following ICD10 codes:

I63x: Cerebral infarction

Overall stroke is defined by the following ICD10 codes:

I60x: Subarachnoid haemorrhage

I61x: Intracerebral haemorrhage

I62x: Other nontraumatic intracranial haemorrhage

I63x: Cerebral infarction

I64x: Stroke, not specified as haemorrhage or infarction

Events of systemic embolism will be analysed separately and in combination with ischemic and overall stroke. Systemic embolism is defined by the following ICD10 codes:

I74x: Arterial embolism and thrombosis

All-cause mortality will be analysed separately and in combination with ischemic and overall stroke plus systemic embolism.

Events of myocardial infarction will be analysed separately and is defined by the following ICD10 codes:

I21x: Acute myocardial infarction

I22x: Subsequent myocardial infarction

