CHA ₂ DS ₂ VASc	NPR and NorPD	
 - Chronic Heart Failure by NorPD reimbursement codes for heart failure: I50 (ICD10) or K77 (ICPC). 1 point - Hypertension defined by dispensation of at least one anti-hypertensive drug last year prior to index date (see definition above). 1 point - Diabetes defined by dispensation of at least one anti-diabetes drug last year prior to index date (see definition above). 1 point - Age \geq75 years (2 points) or age 64-74 years (1 point) - Previous stroke, TIA or thromboembolism by ICD10 codes (see definition above). 2 points - Peripheral artery disease (ICD10; I739). 1 point - Gender (male=1 point, female=0 point) 
Total score 0 to 9
	Stroke risk score used as co-variate and effect modifier
Charlson co-morbidity index	NPR and NorPD	
 - Age: \leq41 years (0 point), 41-50 years (1 point), 51-60 years (2 points), 61-70 (3 points), \geq71 years (4 points) - Myocardial infarction. 1 point - Congestive Heart Failure. 1 point - Peripheral Vascular Disease. 1 point - TIA or stroke. 1 points - Dementia. 1 point 	Co-morbidity risk score and co-variate

Variable	data source	Definition	Relevance
		
 - COPD. 1 point - Connective Tissue Disease. 1 point - Peptic ulcer and bleeding 1 point - Diabetes. 1 point - Moderate to severe Chronic Kidney Disease (combined CKD and ESRD). 2 points - Leukemia. 2 points - Lymphoma. 2 points - Solid tumour. 2 points - Liver disease. 3 points - Solid tumour with metastasis. 6 points - AIDS. 6 points Total score from 0 to 37	

Table 5: Additional clinical characteristics to be retrieved for the EMR cohort (cohort 2)

Variable	Data source	Operation definition	Relevance
Height	EMR	Height in centimeters from time point closest to the index date	Co-variate
Weight	EMR	Weight in kilogram from time point closest to the index date	Co-variate
Smoking habits	EMR	Smoking habits retrieved as free text search. Converted to pack-years	Co-variate
Alcohol abuse	EMR	Alcohol abuse search as free text	Co-variate
International normalised ratio	EMR	Retrieve all INR measurements from index to the end of study. Calculated INR mean during the study period	Co-variate. Imputation
Blood haemoglobin	EMR	Retrieve all Hb measurements from index to the end of study. Calculated Hb mean during the study period. Identify episodes of more than 20 g/L fall in hemoglobin	Co-variate. Bleeding endpoint

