9.3.4.2 Safety outcome definitions

Cohort 1:

NPR lacks information on laboratory measurements. Hence, we cannot use the ISTH (International Society of Thrombosis and Hemostasis) definition of a major bleeding episode which include a fall in hemoglobin level of 20 g/L (1.24 mmol/L) or more

The primary bleeding endpoint of intracranial haemorrhage (ICH) is defined by the following ICD10 codes:

I60x Subarachnoid haemorrhage

I61x Intracerebral haemorrhage

I62x Other non-traumatic intracranial haemorrhage

Cohort 2:

The primary bleeding endpoint of intracranial haemorrhage (ICH) is defined by the following ICD10 codes:

I60x Subarachnoid haemorrhage

I61x Intracerebral haemorrhage

I62x Other non-traumatic intracranial haemorrhage

Secondary safety outcome measures in cohort 2 are major bleeds defined by the Cunningham algorithm (11) and the ISTH definition (12) for major bleeds.

The Cunningham algorithm (11) defines a hospitalization with a primary ICD10 code for major bleeding except for ICH where all hospitalizations is counted (> 8 hrs in-patient)(see below).

The Cunningham algorithm is originally based on the ICD-9-CM system. All codes in the ICD-9-CM is not easily converted to ICD9 and later the ICD9 system was replaced by ICD10. Thus, the ICD10 based Cunningham definition will be built on the following outcomes:

Gastrointestinal:

K920	Hematemesis
K921	Melena
K922	Gastrointestinal haemorrhage, unspecified
K226	Mallory-Weiss syndrome
K250/K252/K254/K256	Gastric ulcer with bleeding and/or perforation
K260/K262/K264/K266	Duodenal ulcer with bleeding and/or perforation
K275/K272/K274/K276	Peptic ulcer with bleeding and/or perforation
K285/K282/K284/K286	Peptic ulcer with bleeding and/or perforation
K290	Acute haemorrhagic gastritis
K625	Haemorrhage of anus and rectum
I850	Oesophageal varices with bleeding
I983	Oesophageal varices with bleeding in diseases classified elsewhere

Intracranial:

I60x	Subarachnoid haemorrhage
I61x	Intracerebral haemorrhage
I62x	Other non-traumatic intracranial haemorrhage

Other:

N02	Recurrent and persistent haematuria
H431	Vitreous hemorrhage
K661	Haemoperitoneum
R042	Haemoptysis
R040	Epistaxis
K250	Haemarthrosis
N939	Vaginal bleeding

The ISTH (12) definition for major bleeding in non-surgical patients is defined by one of the following criteria:

1. Fatal bleeding, and/or

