9.4 Data sources

For cohort 1 three data sources will form the basis for the analyses, the Norwegian Census Register (FRG), the Norwegian Prescription Database (NorPD) and the Norwegian Patient Register (NPR). The FRG list all Norwegian residents from birth to death, including migration data and place of birth.

The NorPD is a register covering all prescriptions dispensed at pharmacies nationwide and data is available from 1 January 2004. Each medication is coded according to the Anatomical Therapeutic Chemical (ATC) system. The prescription registry also includes information about date of dispensation, quantity dispensed, the defined daily dose (DDD) of the dispensed drug and strength. NorPD does not cover drug administered during hospital stays, drugs used at nursing home or over-the-counter drugs. From March 2007 the NorPD includes the reimbursement code using either the ICD10 or the ICPC-2 coding systems.

The NPR was established in 2008 and contains all hospital visits (emergency visits, in-patient hospitalizations and outpatient ambulatory consultations), length of stay and procedures (surgical and medical) from all hospitals in Norway. Diagnoses are coded according to the International Classification of Diseases, 10th revision (ICD10). Medical and surgical procedures are coded based on the NOMESCO (The Nordic Medico-Statistical Committee) coding system. Both primary and all subsequent codes related to each admission will be retrieved. Lag time in NPR is approximately 4 months.

The registries are nation-wide and provision of the information is mandatory, which eliminates the risk of both selection and recall bias. The large and detailed dataset also makes it possible to adjust for risk factors and analyze in depth the different sources of bias and confounding. The registry holders will generate the datasets and release it in a coded and de-identified form, but with a unique identifier common to the three datasets making individual merging of the NorPD, NPR and FRG datasets possible.

Data from the registries will be linked using the unique 11-digit national identification number. NorPD is a pseudonymized register and the registry holder will according to national guidelines handle the linkage and release the dataset in a coded form so that all participants remain de-identified.

The following key variables will be retrieved from FRG;

- Age
- Gender (male, female)

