9.6 Data management

There will be 3 main steps;

- Merge together all data and build the analytical dataset
- Create patient cohorts
- Populate tables and figures

Statistical Analysis System (SAS software, version 9.4, SAS Institute, Cary, NC) will be used to all data handling to prepare analytical dataset.

The data from NorPD and NPR are considered high quality register data, however, some quality checking and data cleaning will be done to check for reasonability and consistency of data, e.g. by cross-tabulation of patient characteristics compared to publically available data sources and so forth. From these initial cut of data, further programming will be applied to identify the eligible patient cohorts with additional information of interest to address study objectives as include the following:

- All data from different sources will be retrieved/imported into SAS.
- Completeness of data regarding the number of variables and observations will be verified against the source.
- Quality control of the reasonability and consistency of information and data cleaning will be done
- Datasets will be merged to provide all information needed from various sources to define the patient cohorts.
- Patient cohorts will be defined and include all subjects which fulfills the cohort's inclusion criteria (section 9.2.2).
- Co-morbid conditions of interest within five years prior to index date will be identified, and various co-morbidity scores will be calculated (section 9.3.1).
- Concomitant medications at baseline and during the follow-up according to the ATC codes as described in section 9.3.1 will be selected.

- Adherence to each OAC will be estimated as described in section 9.3.3.
- All outcomes of interest (new events during follow-up) will be selected according to sections 8.1-3 and 9.3.4.1-2.
- Three different subset of cohorts for survival analysis based on exposure to OAC (continuous use or switched) will be defined as described in section 9.3.2.
- Finally a clean ready-to-use analysis database will be constructed, which will contain complete set of all data including the derived variables, according to the study protocol.
- Tables and figures will be populated

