9.7.1 Analysis of primary outcome(s)

The incidence rates and corresponding 95% confidence intervals for ischemic stroke and intracranial hemorrhage will be calculated for warfarin, apixaban, dabigatran and rivaroxaban cohorts on a confounder adjusted population.

The person time at risk will be calculated from first OAC use during the study period until a certain outcome, death or end of follow-up in June 30, 2018 (or later depending on the availability of data). The incidence rates will be calculated by the number of first cases of a certain event during the follow-up divided by person time at risk and will be presented per 100 (or 1000) patient years with exact 95% Confidence Interval (Poisson distribution) for all outcomes of interest, and separately for each OAC.

To compare outcomes of interest in cohorts of warfarin with apixaban, dabigatran and rivaroxaban users, the incidence rate ratios and corresponding 95% confidence intervals will be calculated.

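### As written, both primary outcomes can be met by follow-up care of a stroke or intracranial bleed that happened before index, because no rule says what makes an event new

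*Protocol*

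**What the plan says.** Both primary outcomes are defined by diagnosis code alone. For effectiveness, section 9.3.4.1 says "The main efficacy endpoint is ischemic stroke defined by the following ICD10 codes" and gives I63x. For safety, section 9.3.4.2 says, for each cohort, "The primary bleeding endpoint of intracranial haemorrhage (ICH) is defined by the following ICD10 codes" and gives I60x, I61x and I62x. Neither text states a type of contact, a diagnosis position, an event-free interval, or how linked stays are joined.

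The outcome source is broad. Section 9.4 says the patient register "contains all hospital visits (emergency visits, in-patient hospitalizations and outpatient ambulatory consultations", and adds: "Both primary and all subsequent codes related to each admission will be retrieved". Section 9.7.1 builds the incidence rate from "the number of first cases of a certain event during the follow-up divided by person time at risk", counting from first OAC use.

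Patients with an earlier stroke or bleed stay in the cohort. Section 9.2.2 excludes valvular AF, venous thromboembolism in the last 6 months and knee or hip replacement in the last 5 weeks, but not stroke or intracranial haemorrhage. Section 9.3.1 treats them as baseline covariates and score items, for example "Previous stroke, TIA or thromboembolism by ICD10 codes (see definition above). 2 points".

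The only wording on novelty is in section 9.6: "All outcomes of interest (new events during follow-up) will be selected according to sections 8.1-3 and 9.3.4.1-2". The sections it points to hold the objectives and the code lists.

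**The concern.** The codes that identify an outcome after index also identify stroke or bleeding history before index. A patient who starts an OAC after a recent stroke, and attends a control visit coded I63 some weeks later, meets the primary definition without having had a second stroke. That visit is correctly coded, so the reassurance about coding errors in section 9.9 does not reach it.

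Such contacts put prevalent events into the numerator of the primary rates. If they are equally common in the two matched groups, the absolute rates are too high and the rate ratio moves towards 1. If time since the event differs by drug, the ratio can be biased in either direction. A larger sample does not reduce either effect.

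**Working it through.** **1. The plan's own figures.** Section 9.5 assumes 70,000 patients, drug shares of 11%, 17% and 19% (dabigatran, apixaban, rivaroxaban) and 90% matched:

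- 70,000 × 0.11 × 0.90 = 6930
- 70,000 × 0.17 × 0.90 = 10710
- 70,000 × 0.19 × 0.90 = 11970

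These are the stated group sizes. With warfarin risks of 2.43% (stroke) and 1.23% (intracranial haemorrhage), exact intervals for proportions and log-scale Wald intervals for relative risks reproduce the maximum widths under Tables 7-10: 0.98%, 0.67, 0.71% and 0.96. The study-size section is not in error on this point.

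**2. Does the text allow a carry-over contact to count?** Four conditions are needed, and the protocol meets each:

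- The patient is eligible: section 9.2.2 has no stroke or bleed exclusion.
- The contact is in the source: section 9.4 includes outpatient and emergency contacts and all diagnosis positions.
- The contact meets the definition: sections 9.3.4.1 and 9.3.4.2 require only the code.
- Nothing later removes it: section 9.6 refers back to the same lists. The in-patient rule in section 9.3.4.2 (more than 8 hours) belongs to the Cunningham definition, a secondary outcome in cohort 2.

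**3. Size under an assumption.** Let f be the share of patients whose first counted event is a carry-over contact. The documents do not give f. It is assumed here to run from 0.25% to 2% and to be equal in both groups. With p0 the planned warfarin risk:

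observed warfarin risk = p0 + f; observed ratio = (p0 × RR + f) / (p0 + f)

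| Outcome | f | Warfarin risk seen | Share of warfarin events that are false | True 0.60 seen as | True 1.80 seen as |
|---|---|---|---|---|---|
| Stroke, p0 = 2.43% | 0.25% | 2.68% | 9% | 0.64 | 1.73 |
| | 0.5% | 2.93% | 17% | 0.67 | 1.66 |
| | 1% | 3.43% | 29% | 0.72 | 1.57 |
| | 2% | 4.43% | 45% | 0.78 | 1.44 |
| ICH, p0 = 1.23% | 0.25% | 1.48% | 17% | 0.67 | 1.66 |
| | 0.5% | 1.73% | 29% | 0.72 | 1.57 |
| | 1% | 2.23% | 45% | 0.78 | 1.44 |
| | 2% | 3.23% | 62% | 0.85 | 1.30 |

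Worked example, stroke at f = 2%: (0.0243 × 0.60 + 0.02) / (0.0243 + 0.02) = 0.03458 / 0.0443 = 0.78. Table 8 plans intervals at a ratio of 0.60 with upper limits of 0.77, 0.73 and 0.72. At the top of the assumed range the shift therefore takes the estimate past all three.

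**4. Unequal carry-over.** If f is 2% on warfarin and 20% higher or lower on the NOAC, a true ratio of 1.00 is seen as (0.0243 + 0.024) / 0.0443 = 1.09 or (0.0243 + 0.016) / 0.0443 = 0.91 for stroke. For intracranial haemorrhage it is (0.0123 + 0.024) / 0.0323 = 1.12 or (0.0123 + 0.016) / 0.0323 = 0.88.

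The sums use 18-month risks, as section 9.5 does, rather than person-time rates. They ignore the few patients who would have both a false and a true event.

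**The case against.** The strongest defence is that the intent is plain. Sections 9.6 and 9.7.1 speak of new events and first cases, and an episode rule could stand in the SAP, which is not at hand. This stands as far as intent goes, so one cannot say that carry-over contacts will be counted, only that the definition as written admits them. It does not dispose of the point. Section 9.7 leaves propensity modelling, matching, missing data and analysis detail to the SAP, but says a major change to a primary endpoint definition would be reflected in a protocol amendment.

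Three stronger readings are tempting, and the documents do not support them.

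- A reader might infer that acute transfers and direct rehabilitation stays are routinely counted. Index is a pharmacy dispensation, and section 9.4 says the prescription database does not cover drugs given during hospital stays. For an in-hospital start, most direct transfers would precede index. Control visits and later re-admissions are the real exposure.
- A reader might infer that the adjustment ignores how recent a stroke was. Section 9.3.1 scores stroke, and critical-organ bleeding, in the year before index within the modified HAS-BLED, which is a covariate. But this is one point each in a composite, it does not separate weeks from months, and balance on it would not remove false events.
- A reader might choose inputs that give a large bias and treat it as expected. Nothing in the documents gives the share of patients with a recent event, how often their later contacts carry the code, or any imbalance left after matching.

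The planned validation of stroke and bleeding endpoints against EMR data (section 8.3) bears on false events. It is exploratory, and section 9.2 makes cohort 2 depend on EMR access being granted.

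**Conclusion.** The point holds as a gap in the definition of both primary outcomes. A correctly coded outpatient visit or later re-admission for a pre-index stroke or intracranial bleed satisfies the text, and no passage removes it. The direction follows from the structure: rates too high and ratio towards 1 if carry-over is equal, either direction if it is not.

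The size is not known. The shifts from 0.60 to 0.64-0.78 (stroke) and 0.67-0.85 (intracranial haemorrhage) rest entirely on the assumed equal share of 0.25-2%. The carry-over share cannot exceed the share of patients with a coded pre-index event, so the upper end for haemorrhage requires at least 2% of starters to have had one, which the documents neither state nor rule out. The definition should be corrected before analysis. The text does not show that the planned results would be invalid.

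**What to change.** In sections 9.3.4.1 and 9.3.4.2, define an incident primary event as an in-patient stay with the listed code, with an admission date after index, that is not contiguous by admission and discharge dates with a stay begun on or before index. State that outpatient contacts do not count. Section 9.4 already requests these dates and the in-patient/outpatient status. It lists no transfer, rehabilitation or acute-admission flag, so the rule should rest on dates.

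Add a sensitivity analysis that excludes patients with I60-I64 in a stated window before index, for example 90 days. This also covers later re-admissions for the old event that a contiguity rule would let through. Time since last stroke or intracranial haemorrhage could optionally be offered as a propensity score covariate in the SAP.

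The cost is wording in two sections, some programming and one extra analysis. The downside is that a few true early recurrences may not be counted, as would events that never led to an in-patient stay.
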